6.3.2.8. Sensitivity Analyses

Sensitivity analyses based on a 2-point, 4-point and 5-point decrease from baseline in FKSI-DRS will be conducted for TTD; similarly, sensitivity analyses based on a 2-point, 4-point and 5-point increase from baseline in FKSI-DRS will be conducted for TTI. Cumulative distribution function plots of the change from baseline in the FKSI-DRS for Cycle 2, 4, 6, 8 and 10 will also be presented.

For TTD and TTI, the primary analyses will include data from baseline up to EOT assessment (not including EOT). Sensitivity analyses for these endpoints will include all assessments from baseline to the end of the safety follow-up period.

6.4. Subset analyses

Subset analyses will be performed for PD-L1 positive patients and for patients unselected for PD-L1 expression.

Subset analyses will be performed for PFS, OR and DR per BICR assessment and OS based on the FAS for the subgroups defined below.

The following subgroups will be defined and used for analyses:

- Randomization stratification factors
 - ECOG PS 0 (Reference) vs 1
 - Geographical Region (United States (Reference) vs Canada/Western Europe vs Rest of the World)
- Age
 - Age < 65 years (Reference)
 - Age ≥ 65 years
- Gender
 - Male (Reference)
 - Female
- Race
 - Caucasian / White (Reference)
 - Asian
 - Black/African American
 - Other

- Ethnicity
 - Hispanic/Latino
 - Non-Hispanic/Latino (Reference)
- Pooled Geographical Region
 - North America
 - Europe (Reference)
 - Asia
 - Rest of the World (Australasia Latin America, Africa and/or Middle East will be included as additional subgroups if including > 10% of the overall randomized population)
- Nephrectomy at baseline
 - Yes (Reference)
 - No
- MSKCC prognostic criteria at baseline (detailed in Section 6.5.1.3)
 - Favorable (Reference)
 - Intermediate
 - Poor
- Heng prognostic criteria at baseline (detailed in Section 6.5.1.3)
 - Favorable (Reference)
 - Intermediate
 - Poor

Subset analyses for PFS, OS and DR will use the primary censoring rules described in Sections 6.1.1.1 and 6.1.2.1. All the subgroup analyses are exploratory. Treatment arms will be compared for PFS and OS using a 2-sided unstratified log-rank test for each subgroup level and the unstratified HR and its corresponding 95% CI will be computed per subgroup level.

All the subgroup analyses will be exploratory; no adjustment for multiplicity will be performed. In the case of a low number of patients within a category (<5% of the randomized population), the categories will be pooled.

To assess the heterogeneity of treatment effects for PFS and OS across the subgroup levels, two Cox regression model will be fitted with PFS or OS, respectively, as the dependent variable and subgroup, treatment, and with and without the treatment-by-subgroup interaction as explanatory variables.

- Model 1: factors + treatment + subgroup
- Model 2: factors + treatment + subgroup + treatment×subgroup-variable

A p-value for the interaction test (Likelihood Ratio test) will be provided together with the HR and corresponding 95% CI for the interaction model parameter.

The HR for PFS and OS and corresponding 95% CIs for all subgroups will also be presented in a forest plot.

The ORR odds ratio for each subgroup and corresponding 95% CIs will also be presented in a forest plot for each treatment arm.

6.5. Baseline and Other Summaries and Analyses

6.5.1. Baseline summaries

The following analyses will be performed for PD-L1 positive patients and for patients unselected for PD-L1 expression and will be based on the FAS overall and separately by treatment arm.

6.5.1.1. Demographic characteristics

Demographic characteristics and physical measurements will be summarized by treatment arm using the following information from the ‘Screening/Baseline Visit’ eCRF pages.

- Demographic characteristics
 - Gender: Male, Female
 - Race: White, Black or African American, Asian, American Indian or Alaska Native, Native Hawaiian or other Pacific Islander, Other, Unknown
 - Ethnic origin: Hispanic/Latino (Yes/No)
 - Age (years): summary statistics
 - Age categories:
 - < 65 years, ≥ 65 years
 - <65, 65-<75, 75-<85, ≥ 85 years
 - Pooled Geographical Region (as applicable):
 - North America
 - Europe
 - Asia

- Rest of the World (Australasia, Latin America, Africa and/or Middle East will be included as additional pooled geographical regions if including > 10% of the overall randomized population)
- Geographic Region (as applicable):
 - North America
 - Latin America
 - Western Europe
 - Eastern Europe
 - Middle East
 - Australasia
 - Asia
 - Africa
- Eastern Cooperative Oncology Group (ECOG) Performance Status: 0, 1, 2, 3, and 4
- Physical measurements
 - Height (cm)
 - Weight (kg)
 - Body Mass Index (BMI) (kg/m²)

Center codes will be used for the determination of the patient's geographic region.

The listing of demographics and baseline characteristics will include the following information: patient identifier, treatment arm, age, sex, race, ethnicity, height (cm), weight (kg), BMI (kg/m²), and ECOG performance status.

6.5.1.2. Medical history

Medical history will be coded using the most current available version of Medical Dictionary for Regulatory Activities (MedDRA) and will be summarized from the 'Medical History' eCRF page. Medical history will be summarized as the numbers and percentages of patients by MedDRA preferred term (PT) as event category and MedDRA primary system organ class (SOC) as summary category. Each patient will be counted only once within each PT or SOC.

Medical history will be displayed in terms of frequency tables: ordered by primary SOC and PT in alphabetical order.

6.5.1.3. Disease characteristics

Information on disease characteristics collected on 'Primary Diagnosis', 'Substance Abuse' and RECIST eCRF pages will be summarized overall and by treatment arm. Summary statistics will be presented for the following.

From the 'Primary Diagnosis' eCRF page:

- Site of primary tumor
- Primary diagnosis (summarize all categories collected in the 'Primary Diagnosis' eCRF page)
- Time since initial diagnosis to date of randomization (months), defined as (date of randomization – date of initial diagnosis)/30.4375
- Time since diagnosis of local/regional/distant recurrence of disease (months), defined as (date of randomization – date of diagnosis of local/regional/distant recurrence of disease)/30.4375
- Type of disease recurrence
- Histopathological and Furhman grade
- TNM and AJCC TNM, both at initial diagnosis and current stage
- Prior nephrectomy
- Memorial Sloan-Kettering Cancer Center (MSKCC) prognostic criteria (Motzer et al., 2002)

MSKCC prognostic criteria are based on the detection of five risk factors: ECOG PS ≥ 2 , high LDH (> 1.5 times the ULN), serum hemoglobin $< LLN$, high corrected serum calcium (> 10 mg/dL), time from initial diagnosis to study treatment start less than one year. Patients will be assigned to one of the following risk groups:

- Favorable (0 risk factors)
 - Intermediate (1 or 2 risk factors)
 - Poor (3 or more risk factors)
- Heng prognostic criteria (Heng et al., 2009)

Heng criteria are based on the detection of the same risk factors evaluated by the MSKCC criteria, except for LDH, with the addition of: absolute neutrophils count $> ULN$, platelets count $> ULN$. Patients will be assigned to one of the following risk groups:

- Favorable (0 risk factors)
- Intermediate (1 or 2 risk factors)

- Poor (3 or more risk factors)

From the RECIST eCRF page (summary will be presented separately based on investigator assessment and BICR assessment):

- Measurable disease (lesions) at baseline (Yes, No)
- Involved tumor sites at baseline

From the ‘Substance Use’ eCRF page:

- Smoking history
 - Never smoker vs current vs former smoker
 - Smoking exposure (pack-years): 0, <20, 20-<40, ≥40 and summary statistics
 - Years since quitting: never smoker, current smoker, <5, 5-<10, ≥10 and summary statistics

Specifications for computation:

- Cigarette equivalents are calculated as follows: one cigar is regarded equivalent to 5 cigarettes and 1 pipe is regarded equivalent to 3 cigarettes
- Duration of nicotine consumption [years]:
 $(\text{end of nicotine consumption} - \text{start of nicotine consumption} + 1) / 365.25$
- Pack-years:
 - calculate cigarette equivalents per day using the conversion factors given above
 - convert to packs per day where 20 cigarettes are regarded as 1 pack
 - pack-years = packs per day × duration of nicotine consumption [years]

Listing of disease history will be provided with all relevant data (as collected on the ‘Primary Diagnosis’ and ‘Substance Use’ eCRF pages) and derived variables as above.

6.5.1.4. Prior anti-cancer therapies

The prior anti-cancer therapies are collected under the ‘Prior Cancer Therapy’, ‘Prior Radiation Therapy’ and ‘Prior Surgery’ eCRF pages.

Prior anti-cancer therapies will be included in the listings that follow with a flag to identify prior therapies. These will include the patient identification number, and all the relevant collected data-fields on the corresponding eCRF pages.

- Listing of anti-cancer drug therapies
- Listing of anti-cancer radiotherapy

- Listing of anti-cancer surgeries

6.5.2. Study conduct and patient disposition

The following analyses will be performed based on the FAS overall and separately by treatment arm.

6.5.2.1. Patient disposition

The percentages below will be calculated based on the number of patients in the FAS.

- Total number of patients screened overall
- Number of patients who discontinued from the study prior to randomization overall and by the main reason for discontinuation
- Number and percentage of randomized patients in each of the analysis sets defined in Section 4
- Number and percentage of randomized patients with study drug ongoing (separately for each study drug in Arm A)
- Number and percentage of randomized patients who discontinued study drug overall and by the main reason for discontinuation of study drug (separately for each study drug in Arm A)
- Number and percentage of patients who entered follow-up
- Number and percentage of patients who discontinued follow-up overall and by the main reason for discontinuation
- Number and percentage of patients who entered long-term follow-up
- Number and percentage of patients who discontinued long-term follow-up overall and by the main reason for discontinuation.

The results of the randomization algorithm (according to IRT) will be summarized as follows:

- Number and percentage of randomized patients overall, by region (Europe, EEA (required by EudraCT), North America, Latin America, Middle East, Asia, Australasia, Africa), by country within region
- Number and percentage of randomized patients by center
- Number and percentage of randomized patients by randomization strata (IRT)
- Number and percentage of randomized patients by randomization strata (eCRF)
- Cross tabulation: stratum by IRT vs stratum by eCRF

- Cross tabulation: patients randomized (Arm A/Arm B/none) vs patients treated (Arm A/Arm B/none)

In addition, a cross tabulation of patients who have discontinued/are ongoing treatment with avelumab vs patients who have discontinued/are ongoing treatment with axitinib in the combination arm will also be provided.

6.5.2.2. Protocol deviations

All protocol violations that impact the safety of the patients and/or the conduct of the study and/or its evaluation will be reported. These include:

- Patients who are dosed on the study despite not satisfying the inclusion criteria
- Patients who develop withdrawal criteria whilst on the study but are not withdrawn
- Patients who receive the wrong treatment or an incorrect dose
- Patients who receive an excluded concomitant medication
- Deviations from GCP.

The identification of these and other CSR-reportable deviations will be based on the inclusion/exclusion criteria or other criteria presented in the protocol.

6.5.3. Study treatment compliance and exposure

The following analyses will be based on the safety analysis set by treatment arm.

Cycle definitions for study drugs that are administered in combination apply to all the study drugs in the combination. I.e., cycle is patient-dependent, rather than study-drug-dependent when study drugs are administered in combination.

For Cycle X, actual cycle start date for each patient is

- the earliest start date of dosing in the Cycle X day 1 visit CRF exposure page, if the patient received study treatment on that visit (i.e., any study drug with dose>0 at that visit)
- the first day of assessments in the Cycle X day 1 visit, if the patient did not receive study treatment on that visit (i.e., all study drugs had dose=0 at that visit). Use start date in the exposure page if available; if start date is not available then use date of collection of vital signs on Cycle X day 1 visit.

Actual cycle end date for each patient is,

- for all cycles X except the last cycle, actual cycle end date = actual cycle (X+1) start date – 1 day;
- for the last cycle, actual cycle end date = actual cycle start date + 42 – 1 day

Cycle duration (weeks) = (actual cycle end date – actual cycle start date + 1)/7

When summarizing exposure for each study drug, only cycles from first dose of study treatment until the last cycle with non-zero dose of study drug (Arm B) or at least one of the study drugs (Arm A) should be included.

Exposure will be summarized (per cycle and/or overall) as dose received (cumulative dose, actual dose intensity) and as dose received relative to intended dose (relative dose intensity [RDI]).

The derivations below are provided for the following:

- Avelumab administered as a 1-hour IV infusion at a dose of 10 mg/kg once every 2 weeks in 6-week cycles.
- Axitinib administered BID PO at a dose of 5 mg.
- Sunitinib administered 50 mg PO QD on Schedule 4/2.

Analysis of exposure will be based on the calculated actual dose levels:

- Avelumab - total dose / weight
- Axitinib - total dose
- Sunitinib - total dose.

Exposure and compliance will be summarized by cycle and overall for each study drug in each treatment arm.

6.5.3.1. Exposure to avelumab

The dose level for avelumab is calculated as actual dose administered/weight (mg/kg). The last available weight of the patient on or prior to the day of dosing will be used.

Intended duration of treatment with avelumab (weeks) =

$$(\text{end date} - \text{date of first dose of avelumab} + 1) / 7,$$

where end date = start date of last cycle with non-zero dose of avelumab + 42 – 1

Duration of exposure to avelumab (weeks) = (last dose date of avelumab – first dose date of avelumab + 14)/7

Cumulative dose in a cycle or overall is the sum of the actual doses of avelumab received in a cycle or overall, respectively.

Actual Dose Intensity (DI)

- By cycle actual DI (mg/kg/6-week cycle) = [cumulative dose in the cycle (mg/kg)]/[cycle duration (weeks)/6]
- Overall actual DI (mg/kg/6-week cycle) = [overall cumulative dose (mg/kg)] / [intended duration of treatment with avelumab (weeks)/6].

Relative Dose Intensity (RDI)

- Intended DI (mg/kg/6-week cycle) = [intended cumulative dose per cycle] / [intended number of 6-weeks in a cycle] = [30 (mg/kg)] / [1(6-week cycle)] = 30 (mg/kg/6-week cycle)
- By cycle RDI (%) = $100 \times [\text{by cycle actual DI}] / [\text{intended DI}]$
= $100 \times [\text{by cycle actual DI}] / [30 \text{ (mg/kg/6-week cycle)}]$
- Overall RDI (%) = $100 \times [\text{overall actual DI}] / [\text{intended DI}]$
= $100 \times [\text{overall actual DI}] / [30 \text{ (mg/kg/6-week cycle)}]$

6.5.3.2. Exposure to axitinib

The dose level is calculated as actual dose administered (mg/day).

Intended duration of treatment with axitinib (weeks)=

$$(\text{last dose date of axitinib} - \text{first dose date of axitinib} + 1)/7$$

Duration of exposure to axitinib (weeks) =

$$(\text{last dose date of axitinib} - \text{first dose date of axitinib} + 1)/7$$

Cumulative dose is the sum of the actual doses of axitinib received in the study.

Actual Dose Intensity (DI)

- Overall actual DI (mg/week) = [overall cumulative dose (mg)] / [intended treatment duration (weeks)]

Relative Dose Intensity (RDI)

- RDI (%) = $100 \times [\text{overall cumulative dose}] / [\text{intended cumulative dose per week} \times \text{number of weeks from first dose of study drug to last dose of axitinib}]$
= $100 \times [\text{overall cumulative dose}] / [7 \times 2 \times 5 \times \text{duration of exposure to axitinib}]$

6.5.3.3. Exposure to sunitinib

The dose level is calculated as actual dose administered (mg/day).

Intended duration of treatment with sunitinib (weeks) =

$$(\text{end date} - \text{date of first dose of sunitinib} + 1)/7,$$

where end date = start date of last cycle with non-zero dose of sunitinib + 42 – 1

Duration of exposure to sunitinib (weeks) = (last dose date of sunitinib – first dose date of sunitinib + d)/7, where d = 1 if the patient discontinues sunitinib prior to the end of the last cycle or d = 14 otherwise (i.e. d=1 if date of last dose of sunitinib – date of first dose of sunitinib in the last cycle < 28).

Cumulative dose in a cycle or overall is the sum of the actual doses of sunitinib received in a cycle or overall, respectively.

Actual Dose Intensity (DI)

- By cycle actual DI (mg/6-week cycle) = [cumulative dose in the cycle (mg)]/[cycle duration (weeks)/6]
- Overall actual DI (mg/6-week cycle) = [overall cumulative dose (mg)] / [intended duration of treatment with sunitinib (weeks)/6].

Relative Dose Intensity (RDI)

- Intended DI (mg/6-week cycles) = [intended cumulative dose per cycle] / [intended number of 6-weeks in a cycle] = [7×50×4 (mg)] / [1 (6-week cycle)] = 1400 (mg/6-week cycle)
- By cycle RDI (%) = 100 × [by cycle actual DI] / [intended DI]
= 100 × [by cycle actual DI] / [1400 (mg/6-week cycle)]
- Overall RDI (%) = 100 × [overall actual DI] / [intended DI]
= 100 × [overall actual DI] / [1400 (mg/6-week cycle)]

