5.2.1. Data handling after the cut-off date

Data after the cut-off date may not undergo the cleaning process and will not be displayed in any listings or used for summary statistics, statistical analyses or imputations.

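### Relative dose intensity for avelumab and sunitinib charges the whole last dosed cycle even when the data cut-off or death falls inside it (minor)

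*SAP*

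**What the plan says.** SAP 6.5.3 defines relative dose intensity (RDI) as dose received relative to dose intended, summarised for each drug by cycle and/or overall.

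- **Avelumab (6.5.3.1).** The intended duration runs from first dose to "end date = start date of last cycle with non-zero dose of avelumab + 42" minus one day. Overall dose intensity is "overall cumulative dose (mg/kg)] / [intended duration of treatment with avelumab (weeks)/6", compared with an intended "30 (mg/kg/6-week cycle").
- **Sunitinib (6.5.3.3).** The end date has the same form: "end date = start date of last cycle with non-zero dose of sunitinib + 42" minus one day. Overall dose intensity is "overall cumulative dose (mg)] / [intended duration of treatment with sunitinib (weeks)/6", compared with 1400 mg per 6-week cycle.
- **Axitinib (6.5.3.2).** Intended duration and duration of exposure are the same expression, last dose minus first dose plus one day. The RDI denominator uses the "number of weeks from first dose of study drug to last dose of axitinib".
- **By-cycle figures (6.5.3).** The last cycle has a fixed length: "for the last cycle, actual cycle end date = actual cycle start date + 42" minus one day.
- **Cut-off (5.2.1).** "Data after the cut-off date may not undergo the cleaning process and will not be displayed in any listings or used for summary statistics".

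SAP 5.3.2.4 uses the cut-off date only to fill in a missing last-dose date for ongoing patients. It does not shorten the last cycle. No other section caps the avelumab or sunitinib clock.

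**The concern.** For a patient still on treatment at the cut-off, the avelumab and sunitinib denominators include doses not yet due. SAP 5.2.1 means that those doses can never enter the numerator. The resulting shortfall depends only on where the cut-off falls within the patient's cycle and says nothing about adherence or tolerability. Death inside a cycle has the same effect, because doses scheduled after death are counted as intended. Axitinib stops at its last dose and carries no such charge. A reader who sets the three RDI figures side by side, to ask whether the control was adequately dosed or which Arm A drug was better delivered, would be reading partly a difference in formulas.

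**Working it through.** **Inputs.** Avelumab is given on Days 1, 15 and 29 of a 42-day cycle (Protocol 5.4.1). Sunitinib is given 28 days on and 14 off (Protocol 5.4.3). Axitinib is given twice daily without a break (Protocol 5.4.2). The RDI formulas are those of SAP 6.5.3.1 to 6.5.3.3.

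**The plan's own figures reproduce.** Intended avelumab is 3 × 10 = 30 mg/kg per cycle. Intended sunitinib is 7 × 50 × 4 = 1400 mg per cycle. Intended axitinib is 7 × 2 × 5 = 70 mg per week.

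**Fully adherent patient, cut-off on day d of cycle k.** The intended duration is 42k days, or k six-week units. So:

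- avelumab overall RDI = 10 × (doses given) / (30k)
- sunitinib overall RDI = 50 × [28(k − 1) + min(28, d)] / (1400k)
- axitinib overall RDI = 10 × days / (70 × days/7) = 100%

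| Cycle k | Day d | Avelumab | Sunitinib | Axitinib |
|---|---|---|---|---|
| 1 | 10 | 33.3% | 35.7% | 100% |
| 2 | 10 | 66.7% | 67.9% | 100% |
| 4 | 10 | 83.3% | 83.9% | 100% |
| 8 | 10 | 91.7% | 92.0% | 100% |
| 12 | 10 | 94.4% | 94.6% | 100% |
| any | 28 | below 100% | 100% | 100% |
| any | 29 or later | 100% | 100% | 100% |

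The shortfall exists only while the last cycle's dosing is incomplete, and it falls as 1/k. Averaged over a cut-off day uniform on 1 to 42, RDI at k = 8 is 95.8% for avelumab and 96.0% for sunitinib.

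By-cycle RDI for the last cycle is not diluted by k. A cut-off on Day 10 gives sunitinib 500/1400 = 35.7% for that cycle, whatever its number.

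**Size across a trial population.** Assumptions: uniform accrual over 21 months; exponential time on treatment with the planning PFS medians of 11 months (sunitinib) and 16.9 months (avelumab); no missed doses; deaths not modelled separately. The cut-offs are months 25 and 32, the interim and final PFS times in SAP Table 7 when the hazard ratio is 0.65. The uncapped mean and the ongoing patients' mean RDI come from simulation. With λ = ln 2 / median and cut-off c, the share still on treatment is [exp(−λ(c − 21)) − exp(−λc)] / (21λ). The artefact in the overall mean is that share times the ongoing patients' mean shortfall.

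| Drug, cut-off | Mean RDI as written | Share ongoing | Mean RDI, ongoing | Artefact (points) |
|---|---|---|---|---|
| Sunitinib, month 25 | 91.6% | 0.43 | 95.8% | 0.43 × 4.2 = 1.8 |
| Avelumab, month 25 | 92.9% | 0.57 | 95.9% | 0.57 × 4.1 = 2.3 |
| Sunitinib, month 32 | 92.3% | 0.28 | 97.5% | 0.28 × 2.5 = 0.7 |
| Avelumab, month 32 | 93.8% | 0.43 | 97.6% | 0.43 × 2.4 = 1.0 |

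With the cap, the month-25 means become about 93.5% (sunitinib) and 95.3% (avelumab). The rest of the gap to 100% comes from patients who stop treatment mid-cycle, which the cap leaves unchanged.

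**Why elapsed time cannot simply be cut short.** On a clock ending at the last dose, sunitinib after one full block gives 1400 mg over 4 weeks: 1400/(4/6) = 2100, and 2100/1400 = 150%. The denominator has to count scheduled doses.

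**The case against.** The case for leaving the rules alone is substantial. Charging a whole cycle is a recognised convention and suits a 4-weeks-on, 2-weeks-off schedule. A first-to-last-dose clock is natural for continuous daily axitinib. RDI is descriptive: SAP 6.5.3 plans no test on it, and it does not define the per-protocol set. Tolerability is reported separately through dose reductions, interruptions, delays and discontinuations. All of this stands, and it keeps the point minor. It does not justify charging doses that fall after the cut-off or after death.

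Three stronger readings are tempting, and the documents do not support them.

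- *Full adherence always scores below 100% for two drugs.* It does not. The score is exactly 100% once the last cycle's dosing is complete.
- *A toxicity stop on Day 10 of Cycle 1, scored 36% for sunitinib and 100% for axitinib, shows an error in the sunitinib rule.* That patient did not receive the intended cycle, so charging it is legitimate. The gap shows that axitinib follows a different convention.
- *The formulas make the comparator look under-dosed.* Avelumab, in the experimental arm, is affected to almost the same degree.

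Moving axitinib to the end-of-cycle clock would not equalise matters either. A Day 10 stop would score axitinib 10/42 = 24% against sunitinib's 36%, and a Day 28 stop 28/42 = 67% against 100%.

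**Conclusion.** The point holds as a minor one. Avelumab and sunitinib RDI, overall and for the last cycle, count doses scheduled after the cut-off or death as intended. Ongoing fully adherent patients are understated when the cut-off precedes Day 29 or Day 28 respectively. They average about 96% at month 25 and 97 to 98% at month 32, and overall mean RDI is lowered by about 2 and 1 percentage points.

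These sizes rest on uniform accrual, where the SAP expects non-uniform accrual, and on planning PFS medians standing in for time on treatment. In practice treatment can end earlier for toxicity or continue past progression. The direction and the day thresholds follow from the formulas alone. The axitinib figure is not wrong for a continuous drug, but it answers a different question and should not be compared directly with the other two. PFS and OS analyses are untouched.

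**What to change.** - **Overall RDI, avelumab and sunitinib.** Define intended dose as the doses scheduled (avelumab Days 1, 15 and 29; sunitinib dosing days 1 to 28) from first dose to the earliest of the end of the last dosed cycle, the data cut-off and death. Count scheduled doses, not elapsed days.
- **By-cycle RDI.** Cap the last cycle in SAP 6.5.3 in the same way.
- **Mid-cycle stops.** Keep the whole-cycle charge for patients who discontinue before the cut-off.
- **Axitinib.** Leave the formula. Footnote that its clock ends at the last dose, that stops and unresumed holds are therefore not charged, and that its RDI should not be compared directly with that of avelumab or sunitinib.

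The cost is a few lines of SAP wording, a small programming change and one table footnote. No extra data are needed.

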#### **5.4.3. Sunitinib**

Sunitinib will be administered orally QD at approximately the same time daily continuously for 4 consecutive weeks followed by a 2-week off-treatment period (Schedule 4/2 in 6-week cycles), Sunitinib capsules are to be taken daily and may be administered without regard to meals. Capsules must not be opened, split, or dissolved, and patients should be instructed to swallow the study medication whole without manipulation or chewing of the medication prior to swallowing.

A dosing card will be provided to the patients to provide guidance for the correct use of sunitinib.

Patients must be instructed that if they miss a dose or vomit anytime after taking a dose, they must not “make it up” with an extra dose, but instead resume subsequent doses as prescribed. Any missed dose may be taken late in the same day, otherwise, it should be skipped and dosing resumed with subsequent doses as prescribed. Patient must be instructed to record all doses (missed or vomited doses or extra doses) in a dosing diary supplied by the site. If doses are missed or vomited or if an extra dose is taken, this must be indicated in the source documents and CRFs.

Patients experiencing toxicity may require treatment adjustment or discontinuation according to the guidelines specified in Table 2 and Table 4.

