#### **5.4.6.4. Axitinib Dose Modifications, Avelumab Infusion Omissions, and Sunitinib Dose Modifications for Treatment-Related Toxicity**

In Arm A, recommended axitinib dose modifications and avelumab infusion omissions in case of drug related toxicity are shown in Table 3. The aforementioned guidelines might be further modified at the discretion of the sponsor based on the emerging safety profile of the combination. The investigator can consider consulting with the sponsor's medical monitor in case of persistent toxicity that would lead to dose modification or treatment discontinuation per toxicity treatment guidelines.

In Arm B, recommended sunitinib dose modifications in case of drug-related toxicity are shown in Table 4.

The 4-week sunitinib dosing period may not be extended to compensate for interruptions in sunitinib treatment due to any cause. If recovery to Grade  $\leq 1$  toxicity does not occur within 6 weeks, investigator should consider consulting with the medical monitor about any dose modification or treatment discontinuation.

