5.3.2.4. Exposure

No imputation will be done for first dose date. Date of last dose of study drug, if unknown or partially unknown, will be imputed as follows:

- If the last date of study drug is completely missing and there is no End of Treatment eCRF page and no death date, the patient should be considered to be ongoing and use the cut-off date for the analysis as the last dosing date
- If the last date of study drug is completely or partially missing and there is EITHER an End of Treatment eCRF page OR a death date available (within the cut-off date), then imputed last dose date is:
 - = 31DECYYYY, if only Year is available and Year < Year of min (EOT date, death date)
 - = Last day of the month, if both Year and Month are available and Year = Year of min (EOT date, death date) and Month < the month of min (EOT date, death date)
 - = min (EOT date, death date), for all other cases

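### SAP 6.5.3.3: the numeric test for d in the sunitinib duration of exposure is off by one, so an on-schedule Day 1 to Day 28 course can never reach d = 14

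*SAP*

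**What the plan says.** SAP 6.5.3.3 defines duration of exposure to sunitinib, in weeks, as (last dose date − first dose date + d)/7, "where d = 1 if the patient discontinues sunitinib prior to the end of the last cycle or d = 14 otherwise". A parenthesis restates the condition numerically: d = 1 when the last dose date minus the "date of first dose of sunitinib in the last cycle < 28".

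The same section defines a separate intended duration of treatment. Its end date is the "start date of last cycle with non-zero dose of sunitinib + 42", minus 1. SAP 6.5.3 closes the final cycle the same way: "for the last cycle, actual cycle end date = actual cycle start date + 42 – 1 day". Both make the last cycle 42 days.

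The protocol limits dosing to four weeks of each cycle. Section 5.4.6.4 says "The 4-week sunitinib dosing period may not be extended to compensate for interruptions", and section 5.4.3 says "Any missed dose may be taken late in the same day, otherwise, it should be skipped".

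SAP 5.3.2.4 imputes missing last-dose dates. Where neither an end-of-treatment record nor a date of death exists, the instruction is that "the patient should be considered to be ongoing and use the cut-off date for the analysis as the last dosing date". With either of these available, the date becomes the end of a year or month, or the earlier of the end-of-treatment and death dates.

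**The concern.** The parenthesis is offered as a restatement of the rule in words, but it does not pick out the same patients. The d = 14 branch evidently exists to credit the two-week rest period to a patient who finished the four-week dosing period. A threshold of 28 on a difference between two dates asks for a last dose on Day 29, and the schedule has no dose on that day. The branch therefore misses the patients it was written for. It can still catch patients whose last-dose date was imputed into the rest period, for whom adding 14 days has no basis.

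At stake is the duration of exposure reported for Arm B, which is set beside durations for avelumab and axitinib that do reach 42 days for a full cycle. Two programmers, one following the words and one the numeric test, could also produce different tables.

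**Working it through.** **Inputs**

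- Days counted = last dose date − first dose date + d (SAP 6.5.3.3).
- Numeric test: d = 1 if the difference within the last cycle is below 28, otherwise 14 (SAP 6.5.3.3).
- Schedule: four weeks on, two weeks off (Protocol 3.1.1 and 5.4.3).
- Last cycle: 42 days (SAP 6.5.3, and the intended duration in 6.5.3.3).

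**Step 1: the length of the dosing period.** SAP 6.5.3.3 gives an intended dose of 1400 mg per cycle. This reproduces: 7 × 50 × 4 = 1400, and 1400/50 = 28 dosing days. An on-schedule course is therefore Day 1 to Day 28.

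**Step 2: one cycle, first dose on Day 1, rule as printed**

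| Last-dose date | Difference | d | Days counted | Days counted beyond the last-dose date |
|---|---|---|---|---|
| Day 27 | 26 | 1 | 27 | 0 |
| Day 28 | 27 | 1 | 28 (4.00 weeks) | 0 |
| Day 29 | 28 | 14 | 42 (6.00 weeks) | 13 |
| Day 35 | 34 | 14 | 48 (6.86 weeks) | 13 |
| Day 42 | 41 | 14 | 55 (7.86 weeks) | 13 |

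At Day 28, 27 is below 28, so d = 1. With d = 14 the result would be 27 + 14 = 41 days (5.86 weeks). The two branches differ by 41 − 28 = 13 days. Against the 42-day cycle the shortfall is 42 − 28 = 14 days. The printed rule returns exactly 42 only at a difference of 28, the mark of an inclusive-day slip.

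**Step 3: n cycles on schedule, last dose recorded on Day 28 of cycle n.** The rule gives 42(n − 1) + 28 days, against 42n.

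| n | As printed | With d = 14 | 42n | Shortfall from 42n |
|---|---|---|---|---|
| 1 | 28 | 41 | 42 | 14/42 = 33.3% |
| 2 | 70 | 83 | 84 | 14/84 = 16.7% |
| 5 | 196 | 209 | 210 | 14/210 = 6.7% |
| 10 | 406 | 419 | 420 | 14/420 = 3.3% |

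**Step 4: the other drugs over one full cycle.** Avelumab uses ("last dose date of avelumab – first dose date of avelumab + 14)/7": infusions from Day 1 to Day 29 give 28 + 14 = 42 days. Axitinib uses +1 but is dosed daily: 41 + 1 = 42 days. Sunitinib gives 28.

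**Step 5: effect on the Arm B mean.** The documents do not give the share p of Arm B patients with a recorded Day 28 last dose, so these shares are assumptions. The understatement is 13p/7 weeks against d = 14, or 2p weeks against the 42-day cycle. For p = 10%, 25% and 50% this is 0.19, 0.46 and 0.93 weeks, or 0.2, 0.5 and 1.0 weeks. These are not net effects, because imputed dates in the rest period push the mean the other way.

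**The case against.** The strongest defence is that the words and the test need not conflict. The words turn on stopping before the end of the last cycle, and SAP 6.5.3 ends that cycle on Day 42. A patient last dosed on Day 28 and withdrawn on Day 35 could literally be someone who stopped before the end, so d = 1 would be right. It is fair that the wording is ambiguous. But on that reading d = 14 applies to no on-schedule patient and has no evident purpose, so the rule is defective either way.

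Two limits on size also stand. The gap between the SAP's two branches is 13 days. The 14-day and 2p-week figures rest on the intended duration, which the SAP defines as a separate quantity. And 55 days is only the Day 42 result, not a maximum, since an end-of-treatment or death date used for imputation may fall later.

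A reader might infer that the remedy is simply to give d = 15 to everyone with a difference of 27 or more, capped at 42 days for the last cycle. That would be wrong for imputed dates. A cut-off on Day 28 used as the last-dose date is counted correctly today as 28 days. The blanket change would make it 42, and a cut-off or death on Day 29 or 35 would likewise be credited with 13 or 7 days after that date.

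**Conclusion.** Wrong as written; minor. The numeric test denies d = 14 to every recorded on-schedule course. A patient who completes the dosing period is counted 28 days for the last cycle: 13 days fewer than d = 14 would give, and 14 fewer than the SAP's 42-day cycle. For imputed dates on Day 29 or later, it adds 13 days beyond the imputed date.

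The arithmetic assumes that the first dose of the last cycle is on its Day 1; the multi-cycle figures also assume that earlier cycles ran to schedule.

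A reader might infer that sunitinib dose intensity, or the safety comparison between arms, is distorted. The documents do not support that. Sunitinib dose intensity and relative dose intensity divide by the intended duration or by cycle duration. The on-treatment period (SAP 5.2.7) runs from the dose dates and the start of new therapy, and AE percentages count patients. None of these, and no efficacy endpoint, uses d. Nor can one say that Arm B exposure is understated by two weeks overall: the share affected is unknown and the errors run in both directions.

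**What to change.** In SAP 6.5.3.3:

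1. **Recorded last-dose dates.** Set d = 1 if the difference within the last cycle is below 27, otherwise d = 15. Day 27 then gives 26 + 1 = 27 days and Day 28 gives 27 + 15 = 42. Changing only the threshold and keeping d = 14 would give 41.
2. **Last-dose dates imputed under SAP 5.3.2.4.** Use d = 1, so that imputed dates on Days 28, 29, 35 and 42 give 28, 29, 35 and 42 days and nothing is credited after the cut-off, end-of-treatment or death date used.
3. **Cap.** In both cases, do not let duration of exposure exceed the intended duration already defined in 6.5.3.3. A dose recorded off schedule on Day 29 (28 + 15 = 43) is then held at 42.
4. **Wording.** Replace the reference to the end of the last cycle with completion of the 28-day dosing period.

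Two features remain and should be stated. There is still a step between Day 27 and Day 28, as the branch structure implies; any tolerance should be written down. A recorded Day 28 last dose is credited with the full rest period even if the cut-off or death falls within it, just as the avelumab formula always credits 14 days from its last dose.

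The cost is a few lines of text and programming. No new data are needed: the intended duration is already derived, and SAP 5.3.1 already calls for imputed values to be flagged in listings.
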